Intervention: The Coach2Move approach is stepwise implemented in 16 physiotherapy practices. On each site, at least one physiotherapist in geriatrics and one physiotherapist will receive a two-day training in the Coach2Move approach, which makes use of elements of the Hypothesis Oriented Approach for Clinicians (HOAC-II) and the International Classification of Functioning and Health (ICF). Participants receive physiotherapy according to the Coach2Move approach instead of the usual care physiotherapy.

Main study parameters/endpoints: In this study, each participant is measured four times. The first, being the baseline measurement (T0) is prior to physiotherapeutic treatment, while the second is directly after ending the treatment (T1). The following two are respectively six- (T2) and twelve months (T3) after the moment the participant started the treatment.

The primary outcome measures are the cost per quality-adjusted life year (QALY) gained, mobility measured by the modified Timed up and Go (TUG) and the level of moderate physical activity (LAPAQ). Secondary outcomes include: quality of life (EQ-5D), the degree of frailty (Evaluative Frailty Index for Physical activity), perceived effect (Global Perceived Effect and Patient Specific Complaints) and health care utilization costs.

In addition, qualitative data of experiences in implementation of Coach2Move will be gathered from interviews with patients and focus groups with PTG's and PTs.

The quantitative analysis will be based on quality indicators of medical records of patients for each physiotherapist scored by the researcher. The files in the control period are compared with those after implementation of Coach2Move.

Nature and extent of the burden and risks associated with participation, benefit and group relatedness: The physiotherapeutic process according to the Coach2Move strategy does not have more risk compared to usual care physiotherapy. The additional load related to the study participants are being exposed to consists of the three measurement moments in which questionnaires are being conducted. These moments each will take the patients approximately 60 minutes.

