The TUG is a measurement for functional mobility. The TUG is a test commonly used in PT(G) care and allows international comparison. During the test, the patient is instructed to rise out of a chair, walk 4 meters, turn, walk back and sit down on the chair. This procedure is timed. The average time in seconds this takes is the score on this test. Due to limitations of place in housing of patients, the test we use is slightly modified: patients are required to walk 3 meter instead of the usual 4. Outcome is the amount of time in seconds it takes to complete this test. Gait speed has shown to be a reliable proxy indicator for the physical condition of older adults [26].

Another aspect of this study is the investigation of the potential efficiency of the Coach2Move strategy compared to usual care physiotherapy in frail elderly patients referred to physiotherapy by a physician or patients that enter the physiotherapy practice by direct access. The study perspective is societal. The informal caregiver is included in this economic evaluation. The economic evaluation is based on the general principles of a cost-utility analysis.

Primary outcome measures for the economic evaluation, considering the 12 months follow-up period are costs and direct and indirect and QALYs (EQ-5D, derived from the EuroQoL). The incremental cost-effectiveness ratio (ICER) “cost per QALY gained” will be computed and uncertainty surrounding this ICER will be determined using a non parametric bootstrap method. A cost-effectiveness acceptability curve will be derived that is able to evaluate efficiency by using different thresholds (Willingness to Pay) for a QALY gained. The impact of uncertainty surrounding deterministic parameters on the ICER will be explored using one-way sensitivity analyses on the range of extremes.

The cost analysis measures on patient level, volumes of care (consisting of the production factors: personnel, materials and capacity in a prospective way using patient/caregiver based diaries and therapist scoring sheets [CRFs]). Per arm full cost prices will be determined using

real costs of participating practices. If not available, standard cost prices according to the Dutch guidelines for costing research will be used.

Certain procedures standard cost prices are not available real cost prices will be determined using activity based costing. This approach applies to the health care production part of the economic evaluation.

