During the follow-up period costs of informal caregivers will be estimated using a caregiver-based diary (adapted version of van den Berg et al., 2006) [27] and a questionnaire on 3 months recall basis in line with the follow-up pattern of the clinical trial [28]. The friction cost-method will be applied following the Dutch guidelines for costing research [29].

Also medical costs and travel time to health care providers and related costs that patients and caregivers make will be considered (also on the basis of a diary combined with 3 months recall). Utilities from the EQ-5D will be transformed in QALY's using the trapezium method.

a.II Secondary study parameters/endpoints

To measure the level of frailty and participation the Evaluative Frailty Index (EFIP) is used. The Frailty Index is a 50-item questionnaire on deficits in health (signs, symptoms and disabilities) in multiple domains (physical, psychological, social and general health status). This Frailty Index is based on the literature and refined in Delphi rounds. It was sensitive to change in both the pilot- and the trial study. The content validity is good, psychometric properties were be tested alongside the earlier study [30]. The score on this questionnaire is expressed as the ratio of deficits present to the total number of deficits considered.

The Global Perceived Satisfaction and Effect (GPE) score is used to measure patients' satisfaction about the intervention and the perceived effect on a 7-point Likert scale ranging from very unsatisfied to very much satisfied and very much deterioration to very much improvement, respectively [31].

The Patient Specific Complaints Scale (PSC) is commonly used in PT(G) and measures the functional status of a patient. The patient selects up to three most important mobility problems in daily life, which are the most important goals to improve. The degree of hinder is scored by the patient on a 10 point numeric scale [32]. A higher score indicates a higher level of difficulty experienced in the activity mentioned.

The quality of life is tested by usage of EQ-5D questionnaire [33]. This questionnaire consists of six questions comprising 5 domains: mobility, self care, daily activities, pain and emotions. The EQ-5D is recommended where a more concise assessment is required, particularly where a substantial change in health is expected [34].

At baseline comorbidities are registered using the Cumulative Illness Rating Scale-Geriatrics (CIRS-G) [35].

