Another aspect of the study is to evaluate the fidelity of the PT(G)'s to Coach2Move. This is done by the scoring of quality indication scores of patient files. PT(G)'s are asked to assess patients conform the Coach2Move approach. This asks for an extensive and thorough intake to require optimal clinical reasoning during the therapeutic process.

By scoring the files on integrality of data, it can give insight in the diagnostic therapeutic process before and during the implementation of Coach2Move. Scoring will be independently carried out by two researchers. Of every participating therapist, 10 files will be scored: 5 during the control period and 5 during the implementation period.

b. Randomisation, blinding and treatment allocation

Coach2Move is rolled-out sequentially to 4 groups; each comprising 4 physiotherapy practices. The time points at which the different practices receive Coach2Move are determined at random.

Randomisation will be carried out by a random number generator operated by an external independent researcher. By the end of the trial, all practices will have implemented Coach2Move (Figure 1).

Blinding takes place at patient level. Although patients receive an information letter prior to participation, the exact goal of the study is not specified to make sure the expectations are not biased by placement in control- or intervention group. It is stated that the study focuses

on gaining a better understanding in physiotherapeutic treatment among older adults and therefore monitors health before- and after the treatment.

Since the Coach2Move strategy relies heavily on a more extensive and thorough intake including the usage of several questionnaires which otherwise would not be used with regular physiotherapy, it is therefore complicated to blind both the participants as well as the researchers since this study uses outcomes otherwise not obtained.

c. Study procedures

Participating subjects are tested on four occasions: prior to the intervention, after 3, 6 and 12 months after commencement of the intervention.

Subjects are exposed to several questionnaires on the four moments of testing. One physical test is carried out on each of these four moments.

Procedure of patients in the study:

1. Registration at physiotherapy practice
2. Information on study
3. Informed consent

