4. First assessment at the start of the intervention (t0) in which a number of measures will be performed. Questionnaires: LAPAQ, EQ-5D, EFIP, PSC and CIRS-G. In addition, the modified TUG is carried out. This assessment will take approximately 60 minutes and is carried out by one of the researchers during the control period or by one of the participating PT(G)'s during the intervention period.
5. Physiotherapy treatment. In either the experimental or the control group, the physiotherapist determines the number of physiotherapy consults that are needed. This is common in physiotherapy. During the intervention period, the patient and the PT(G) will choose the best fitting intervention profile together.
6. The second assessment (t1) at three months after the start of the intervention: questionnaires: LAPAQ, EQ-5D, EFIP, PSC, GPE and healthcare utilization. Again, the modified TUG is carried out. This assessment will take approximately 45 minutes.
7. The third assessment (t2) at six months after the start of the intervention. Questionnaires: LAPAQ, EQ-5D, EFIP, PSC, GPE, healthcare utilization and adherence. The modified TUG is performed. This assessment will also take approximately 45 minutes and is carried out by the researcher.
8. The fourth assessment (t3) at twelve months after the start of the intervention. Questionnaires: LAPAQ, EQ-5D, EFIP, PSC, GPE, healthcare utilization and adherence. The modified TUG is carried out once again. This assessment will also take approximately 45 minutes and is carried out by the researcher.

A randomised selection of participants is asked to join in focus group meetings to share experiences on Coach2Move. Participation is voluntarily.

All participants will be debriefed after the study by sending an information brochure concerning the most important outcomes and conclusions of the study. In addition, the participating practices for physiotherapy will be sent the same information in flyer format, which they can hang in a visible spot in their practice. Dutch magazines and newspapers will be approached to publish the research outcomes, as has happened during the previous trial of Coach2Move.

Procedure of enrolled therapists in the study:

1. Start with physiotherapeutic care as usual.
2. Electronic medical record (EPD) will be provided to support clinical reasoning and monitoring the process.

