9. STATISTICAL ANALYSIS

Descriptive statistics (mean, SD, proportions) will be used to report patient and PT(G) characteristics. Results on pre-structured questions on the interviews will be analysed using descriptive statistics (mean, SD, proportions).

The scores on the quality indicators of the patient files will be summarized using descriptive statistics. Descriptive summaries and charts will be produced presenting the quantitative results of the process analysis to help identify patterns of potential incomplete delivery.

a. Primary study parameter(s)

Cost-Effectiveness Analysis (CEA):

The Incremental cost-effectiveness ratio (ICER) “cost per Quality-Adjusted Life Year (QALY) gained” based on EQ-5D utilities will be computed and uncertainty will be determined using an appropriate method such as: the bootstrap method, Taylor expansion or the Fieller confidence interval method. A cost-effectiveness acceptability curve will be derived that is able to evaluate efficiency by using different thresholds (Willingness to Pay) for a QALY.

The cost analysis exists of two main parts. The direct costs of the regular physiotherapy and Coach2Move intervention will be determined on a per patient basis. Further, on patient level, volumes of care will be measured prospectively using medical records and cost questionnaires. Also travel time to the therapeutic sessions and related costs patients make will be considered.

The second part of the cost analysis consists of determining the cost prices for each volume of consumption in order to use these for multiplying the volumes registered for each participating patient. The Dutch manual for costing in evaluation analyses will be used [29]. For units of care/resources where no guideline or standard prices are available real cost prices will be determined. Research has shown that QALY's can be determined by applying a scoring method, such as developed by Versteegh and colleagues, on a meaningful health state classification measure, such as the EQ-5D. By means of the Dutch tariff, valuations can be determined for all possible health states as measured by the EQ-5D [27].

b. Secondary study parameter(s)

Quantitative Data Analysis

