Data analysis to determine the overall effectiveness strategy subsequently involves comparison of the data points in the control section of the wedge with those in the intervention section. Because of the hierarchical design (patients nested within practices or within therapists), multilevel linear and logistic regression analysis will be used to compare the outcomes between treatment groups, with age, sex, comorbidity, frailty level and physical functioning at baseline at the patient level as covariates[13]. Time will be included as a fixed effect according to Donkers et al. [13]. In addition, subgroup analyses will be performed between PT and PTG levels.

c. Other study parameters

Qualitative Data Analysis

Interviews and focus group discussions will be elaborated verbatim (every word captured exactly, each final anonymised transcript will be added to the analysis). A structured thematic approach will be used to analyse the qualitative data.

The analysis will consist of five steps: 1) familiarization and initial coding line by line by two researchers; 2) developing a consolidated codebook; 3) coding and indexing all transcripts against the consolidated codebook, and discussion in the research group to focus on key findings for each study objective; 4) charting overall findings and look at any differences in patients, practices and context in dialogue with the project group and patient panel; 5) synthesis and drawing conclusions. In the analysis phase, descriptive summaries of interview data will be produced presenting the data per practice to help identify patterns.

Synthesizing quantitative and qualitative results:

An overall synthesis of the findings of the process evaluation study will take place to describe the context, the implementation of the intervention and the mechanisms of impact, with the aim of explicating the main trial findings and interrogating the intervention theory. Where data is available, we will test hypotheses based on qualitative analysis quantitatively. We will also, where appropriate, conduct the reverse operation and use quantitative data to focus qualitative analyses. Where data from different sources provide competing narratives or findings, we will make these explicit when reporting and provide a justification of our interpretation in such differences.

Budget Impact Analysis (BIA):

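### The plan does not say whether the 12-month QALY difference behind the primary cost-per-QALY outcome is adjusted for EQ-5D utility at T0

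*Combined protocol and SAP*

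**What the plan says.** Section 1 lists cost per QALY among the primary outcomes, and Section 3 makes cost-effectiveness the main research question.

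- **QALY.** Section 8.a.1 sets the horizon ("Primary outcome measures for the economic evaluation, considering the 12 months follow-up period are costs" and QALYs) and the construction: "Utilities from the EQ-5D will be transformed in QALY's using the trapezium method".
- **ICER.** Section 9.a says that the ratio "based on EQ-5D utilities will be computed and uncertainty will be determined using an appropriate method", and offers bootstrap, Taylor expansion or Fieller. It gives no regression for costs or QALYs and no baseline, practice or period term.
- **Covariates.** The only list is in Section 9.b, under secondary parameters. It describes a multilevel comparison of outcomes "with age, sex, comorbidity, frailty level and physical functioning at baseline at the patient level as covariates". EQ-5D utility is not in it, and the ICER is not mentioned.
- **Data.** Section 8.c gives the T0 battery as "Questionnaires: LAPAQ, EQ-5D, EFIP, PSC and CIRS-G", so T0 utility is available. Healthcare utilisation first appears at the second assessment ("questionnaires: LAPAQ, EQ-5D, EFIP, PSC, GPE and healthcare utilization") and again at the third and fourth.
- **Timing.** Section 8.c states: "Participating subjects are tested on four occasions: prior to the intervention, after 3, 6 and 12 months after commencement of the intervention". Section 1 instead places the second measurement at the end of treatment.
- **Groups.** Section 4 defines them as patients treated before and after the therapists' education. Section 8.c has T0 done by researchers in the control period and by participating therapists in the intervention period.

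**The concern.** The T0 utility is the first point of the area under the curve and can be expected to predict the later points. If the groups differ at T0, an unadjusted area credits or debits that difference to the intervention. Practices, not patients, are randomised, and each patient enters when the practice's condition is already fixed and in a different calendar period from the comparison patients. Balance in T0 utility is therefore not protected by patient-level randomisation.

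At stake is a primary outcome whose denominator is likely to be small, so a modest baseline difference in either direction could change the cost-effectiveness conclusion. Leaving the choice open also allows it to be made after the data are seen.

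**Working it through.** **1. The plan's own figure.** The documents give no precision or power figure for QALYs, costs or the ICER. The nearest is the standard error of 0.21 × SD at ICC 0.10 in Section 6.d. A stepped-wedge model with a practice random intercept and fixed period effects (16 practices, 6 periods, implementation period empty, 5 patients per practice and period) gives 0.213 × SD, which reproduces it. That figure belongs to a model with practice and period terms, which the economic sections do not state.

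**2. Trapezium weights.** With visits at 0, 3, 6 and 12 months (Section 8.c), in years:
- T0: 0.25/2 = 0.125
- T1: (0.25 + 0.25)/2 = 0.25
- T2: (0.25 + 0.50)/2 = 0.375
- T3: 0.50/2 = 0.25

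The sum is 1.

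**3. Carry-over of a T0 difference.** Let d be the T0 utility difference and r the share of it that persists at each follow-up (assumed). The QALY difference due to d alone is d × (0.125 + 0.875r).

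| r | factor | QALY for assumed d = 0.03 |
|---|---|---|
| 0 | 0.125 | 0.004 |
| 0.5 | 0.5625 | 0.017 |
| 0.6 | 0.65 | 0.020 |
| 0.7 | 0.7375 | 0.022 |
| 1 | 1 | 0.030 |

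**4. Sensitivity to T1 timing.** If T1 is at the end of treatment, taken as 1 to 5 months, the T0 weight is 1/24 = 0.042 to 5/24 = 0.208. At r = 0.6 the factor is 0.6 + 0.4 × weight, which is 0.617 to 0.683. For d = 0.03 that is 0.0185 to 0.0205 QALY, so the timing conflict changes the result little at this r.

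**5. Size of a chance difference.** Take the simple contrast of about 200 v 200 patients (Section 4), with ICC 0.10 assumed to hold for utility. In Figure 1 of Section 4, practices in groups 1 to 4 have 1, 2, 3 and 4 control periods and 4, 3, 2 and 1 intervention periods of 5 patients.
- Net weight per practice: 5 × (control periods − intervention periods)/200 = −0.075, −0.025, 0.025 and 0.075.
- Sum of squares over 16 practices: 4 × (2 × 0.005625 + 2 × 0.000625) = 0.05.
- Variance, in SD² units: 0.10 × 0.05 + 0.90 × (2/200) = 0.005 + 0.009 = 0.014.
- SE = √0.014 = 0.118 × SD.

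With an assumed utility SD of 0.20 this is 0.024. At r = 0.6 it carries over as 0.65 × 0.024 = 0.015 QALY.

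**6. What that can do to a ratio (illustration only).** Assume a true gain of 0.02 QALY, a cost difference of 300 and r = 0.5. With d = 0 the ICER is 300/0.02 = 15,000. With d = +0.03 it is 300/0.0369 = about 8,100. With d = −0.03 it is 300/0.0031 = about 96,000.

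**7. Effect of adjustment.** If the group difference persists at the same rate as differences between individuals, linear adjustment for T0 utility removes the contribution of d.

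If instead the difference is an assessor artefact s that affects T0 only, the unadjusted QALY is off by 0.125s. The adjusted one (slope 0.65 at r = 0.6) is off by 0.125s − 0.65s = −0.525s. For s = 0.03 these are +0.004 and −0.016 QALY.

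**The case against.** The strongest reply is that the plan is silent; it does not commit to a raw comparison. The trapezium sentence says how utilities become QALYs, not how groups are compared. Section 9.b adjusts outcomes for comorbidity, frailty and physical functioning, and the frailty index covers physical, psychological, social and general health, which overlaps with EQ-5D. That stands as to wording: a reader might infer that an unadjusted analysis is prescribed, and it is not. But nothing links Section 9.b to the ICER, and a primary outcome should not leave the choice open.

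A reader might also infer that the groups are recruited differently. The documents do not show this. Section 10.b gives one consecutive-patient procedure for both conditions, Section 8.b withholds the exact study goal from patients, and Section 6.b keeps clinical data on those not followed up, to check selection. What the documents do show is different calendar time, enrolment after the condition is set, and a different T0 assessor.

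Chance imbalance is sampling variation that a suitable interval covers, not bias. That is right; for the chance part, adjustment is a gain in precision.

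The assessor difference is the most serious objection. Step 7 shows that a pure artefact in T0 utility would be made worse, and reversed in sign, by adjustment. The documents give no size for such an artefact. It does not defeat the point, but both estimates must be shown.

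**Conclusion.** The point holds as an unspecified element of a primary analysis. Section 9.a should say how T0 utility is handled, and adjustment is the better default with data already collected. The size is 0.017 to 0.022 QALY for an assumed T0 difference of 0.03 with 50 to 70% persistence, direction unknown. Chance alone gives about 0.015 QALY per standard error at an assumed SD of 0.20, ICC 0.10 and r = 0.6. The SD, d, r and the use of this ICC for utility are assumptions; none is in the documents for EQ-5D.

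Three stronger readings are not supported:

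- **The whole T0 difference passes into the QALY.** The share runs from 12.5% to 100% with T1 at 3 months, and is 65% at r = 0.6.
- **The chance SE is 0.21 × 0.20 = 0.042.** That multiplier belongs to the model with practice and period terms, not to the simple contrast.
- **The lack of a T0 cost measure is an equal defect.** Pre-treatment cost is not part of 12-month cost, and no size can be given for the effect of omitting it. Section 8.a.III also records healthcare consumption from patient files, although without a time window. The absence of a defined baseline cost is a limitation to note.

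**What to change.** In Section 9.a, pre-specify that:

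1. incremental QALYs come from a regression of the trapezium QALY on condition, with T0 EQ-5D utility as covariate, alongside the practice and period terms of the main model;
2. this estimate feeds the ICER, the bootstrap (refitted in each resample) and the acceptability curve;
3. the same analysis without T0 utility is reported as a sensitivity analysis, with the T0 assessor difference given as the reason;
4. the lack of a defined baseline cost is stated as a limitation, with no new T0 cost questionnaire.

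Sections 1 and 8.c should also agree on the timing of T1, because it sets the trapezium weights.

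The cost is wording only: no new data, visits or patient burden. If the correlation between T0 utility and the QALY is 0.5 to 0.7 (assumed), adjustment also removes r² = 25 to 49% of residual QALY variance. The downside is the assessor artefact in step 7, which the sensitivity analysis makes visible but does not remove.
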